Study Title: Virtual reality decreases child anxiety and pain as well as caregiver anxiety and pain perception during orthopaedic clinic office procedures

PI: [name]

NCT: NCT05708586

Date of IRB Approval of Protocol Version: 5/8/2023

Title: Virtual reality decreases child anxiety and pain as well as caregiver anxiety and pain perception during orthopaedic clinic office procedures

PI: [name]

Co-Authors: [name], [name], [name]

Background/Significance:

Pain is a complex emotion that is multifactorial in nature. It has been shown that a large component of pain is patient anxiety¹. Decreasing anxiety should subsequently result in a decrease in patients' pain. This has been borne out in numerous studies¹⁻⁷. There has been a gradual progression in the understanding of pain and theories relating to pain perception. The Gate Control Theory proposed by Melzack and Wall in the 1960s states that a person's perception of pain is influenced by the level of attention given to the painful stimulus, the emotion associated with the pain, and the past experience of the pain⁵. This theory was subsequently built on by McCaul and Malott who postulated that people have a limited capacity for attention and pain perception occurs only when one is giving attention to the painful stimulus⁵. The Multiple Resources Theory of Wickens postulates that resources in different sensory systems function independently⁵. Taking these theories into consideration it would follow that providing distraction from painful stimuli should decrease one's pain perception. Distraction can include a variety of modalities depending on the age and cognitive ability of the patient. These distractions can include toys with flashing lights, vibrating implements placed on the skin, and mobile phones or tablets that allow patients to watch videos or play games. These pain mitigation tools have been proven useful in many different areas of healthcare including treatment of burn patients^{1,2,6}, patients undergoing painful dental procedures⁷, and patients undergoing rehabilitative therapy after surgical procedures^{8,9}.

More recently virtual reality (VR) has emerged as a viable option in providing adequate pain relief during medical procedures. It integrates multiple senses (visual, auditory, tactile, and even olfactory) to produce sensory distractions. The theory behind VR and its effect on pain modulation stems from a combination of the previously mentioned theories. Producing sensory distractions during painful procedures results in limited ability for the individual to perceive their pain because of the sensory overload. However, there is a limit to the application of VR and it has been shown to not be as efficacious once a pain threshold has been exceeded⁴. VR that is novel, intense, and unpredictable is most effective for mildly noxious pain experiences⁴.

Pediatric subspecialties are unique in that healthcare workers often have two patients to attend to – the child and the caregiver. In this respect it is vitally important to take into consideration the caregivers' perception of the patient's care as this can play a significant role in the patient-provider relationship. Pediatric orthopaedic surgery clinics are particularly attune to this problem as children often present to clinic and must undergo a variety of procedures including cast removal, pin pulling, and suture or staple removal. While the procedure can be performed fairly quickly with minimal pain, there oftentimes is a significant amount of patient and caregiver anxiety regarding the painful nature of the procedure. These anxieties can result in difficulty in performing procedures and delays in clinic workflows.

One solution currently employed to allay these anxieties and decrease pain during procedures is to involve child life specialists (CLS) to provide distraction techniques during procedures. These can range in scope from simple toys to interactive games. While child life can be extremely helpful in distracting patients during procedures there are limitations to their use. They are not usually readily available during clinic as their services are employed by in a multitude of settings in different physical locations. This can result in delays in the procedure (time it takes the CLS to get to clinic) and delays in clinic work flows. In

addition, CLS can only provide so much distraction. Children are still able to see, feel, and hear their surroundings thus contributing to their anxiety and pain perception. Not only can patients become anxious because of the procedure itself, but parental anxiety can exacerbate the patient's anxiety and subsequent pain perception (REFERENCE). Complicating the use of CLS is the COVID-19 pandemic. Clinics are now contracting services and personnel to limit exposures and subsequent spread of the disease. In light of this, we propose a novel tool to assist in decreasing patient pain during in office procedures – VR technology.

Purpose:

The purpose of this study is to demonstrate that the use of a virtual reality experience can decrease child and caregiver anxiety and pain for simple orthopaedic office procedures.

Outcomes:

Primary Outcome:

The primary outcome will be child pain scores before and after the procedure as assessed by the Children's Faces Pain Scale. This scale has been validated to be used in individuals as young as 4 years old to assess their pain. We will also use the following scales to assess patient anxiety before and after the procedure based on patient age. For patients 7 years and older, the State-Trait Anxiety Inventory for Children (STAIC) will be used. For patients less than 7 years old the Children's Fear Scale will be used to assess anxiety.

Secondary Outcome(s):

Secondary outcome measures will be parental anxiety as assessed by the State-Trait Anxiety Inventory (STAI). This is a validated tool to assess caregiver state (situational) and trait (generalized) anxiety in clinical research settings. The tool will be given to caregivers both before and after the office procedure has been completed.

How do you plan to measure these outcomes?

Patients will be randomized to a control group (parental comfort given during the procedure) and the VR group. Surveys (Wong-Baker FACES pain scale and STAIC or Children's Fear Scale) will be administered to children to assess their pre-intervention pain and anxiety. The STAI will be given to caregivers to assess their pre-intervention anxiety. The procedure will then be performed with the corresponding intervention (control or VR). After the procedure patients and caregivers will again be administered the same survey to assess their post-intervention pain and anxiety. The pre and post-intervention scores will be collected. Descriptive statistics will be used to compare the effect of the interventions

Methods:

Inclusion Criteria: Children age 4years old to 17 years old undergoing cast removal, pin removal, or suture removal in clinic. Parents/caregivers accompanying the participant are also eligible to participate.

Exclusion Criteria:

-History of seizures

- Pregnant, have preexisting binocular vision abnormalities or psychiatric disorders, or suffer from a heart condition or other serious medical condition

-Patients can't have implanted medical devices including cardiac pacemakers, hearing aids and defibrillators

Minimum Age: 4 years old

Maximum Age: 17 years old (For patients, no maximum age for parents)

Number of Subjects to be included in study: 100

Proposed Study Start Date: April 1, 2021

Proposed Study End Date: January 1, 2022

Summary of Human Subject Involvement:

Patients who choose to participate in the study will undergo 3 surveys on the day of their clinic visit. Patients randomized to the control group will not have any increase in their clinic visit time. Patients randomized to the VR group may experience minor prolongation of their clinic visit in order to get the equipment up and running. These delays should not be excessive in relation to the original duration of their clinic visit. In addition, patients in the VR group may rarely have unpleasant feelings related to the VR experience such as nausea or dizziness and a period where they will re-adjust to reality after taking off their headset.

Risks:

Patients undergoing these office procedures generally tolerate them very well. As mentioned above patients undergoing VR as part of their office procedure may rarely experience temporary nausea and/or dizziness with the headset on.

Prolonged use should be avoided, as this could negatively impact hand-eye coordination, balance, and multi-tasking ability temporarily. Adults/guardians and study team should monitor children closely during and after use of the headset for any decrease in these abilities. Patient will be monitored by the study team for five minutes after taking the headset off to make sure they are not experiencing any issues.

Seizures.

Some people (about 1 in 4000) may have severe dizziness, seizures, eye or muscle twitching or blackouts triggered by light flashes or patterns, and this may occur while they are watching TV, playing video games or experiencing virtual reality, even if they have never had a seizure or blackout before or have no history of seizures or epilepsy. Such seizures are more common in children and young people. Anyone who experiences any of these symptoms should discontinue use of the headset.

The headset and controller(s) may contain magnets or components that emit radio waves, which could affect the operation of nearby electronics, including cardiac pacemakers, hearing aids and defibrillators. If you have a pacemaker or other implanted medical device, do not use the headset and controller without first consulting your doctor or the manufacturer of your medical device.

The device is not recommended for children under 13

Confidentiality:

Surveys will be collected by clinic staff and kept in a safe, locked box within the clinic. Access will be granted only to the research team members for data collection and review.

Data Collection:

The following information will be collected for analysis:

- Patient age
- Patient gender
- Patient date of birth
- Diagnosis
- In office procedure (e.g. cast removal, pin removal, suture removal)
- Cast type
- Who removes the cast in clinic (i.e. attending, resident, medical assistant)
- Surgical records associated with the injury (if any)
- State-Trait Anxiety Inventory scores
- State-Trait Anxiety Inventory for Children scores
- Children's Fear Scale scores

Survey Assessments:

Faces pain scale

Faces fear scale

State trait anxiety index

Compensation:

Patients will not be compensated for partaking in the study.

References

1. van Twillert B, Bremer M, Faber AW. Computer-Generated Virtual Reality to Control Pain and Anxiety in Pediatric and Adult Burn Patients During Wound Dressing Changes: *J Burn Care Res.* 2007;28(5):694-702. doi:10.1097/BCR.0B013E318148C96F

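### The protocol's only analysis statement compares the randomised arms descriptively, which does not fit its purpose of demonstrating that VR reduces pain and anxiety

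*Protocol*

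**What the plan says.** The *Purpose* section is confirmatory: "The purpose of this study is to demonstrate that the use of a virtual reality experience can decrease child and caregiver anxiety and pain". Under *Primary Outcome*, "The primary outcome will be child pain scores before and after the procedure". The same heading then adds child anxiety, measured by the STAIC from age 7 and by the Children's Fear Scale below that age. Caregiver anxiety on the STAI is secondary.

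The section *How do you plan to measure these outcomes?* sets a randomised comparison: "Patients will be randomized to a control group (parental comfort given during the procedure) and the VR group". Surveys are given before and after the procedure, and "The pre and post-intervention scores will be collected". The analysis sentence follows: "Descriptive statistics will be used to compare the effect of the interventions".

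No test, model, interval, significance level or between-arm effect measure appears anywhere else in the protocol. *Data Collection* lists variables but no method. *Methods* gives "Number of Subjects to be included in study: 100" without a justification. It also says "Parents/caregivers accompanying the participant are also eligible to participate", so it is not clear whether the 100 counts children only.

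**The concern.** To demonstrate that an intervention lowers pain, the analysis must show that the observed difference is larger than chance would readily produce. Descriptive summaries show the direction and size of a difference and stop there. Followed as written, the conclusion on child pain would rest on two sets of summary scores compared by eye, and the same would hold for child and caregiver anxiety.

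This is not a complaint about detail that belongs in a statistical analysis plan (SAP). Silence on the test or model would have been unobjectionable. Here the protocol names a method for comparing the randomised arms, and that method does not suit the aim. An SAP that specifies an inferential comparison would contradict the sentence, and one that follows the sentence would leave the purpose unmet. The wording has to change in either case.

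**Working it through.** **No figure to reproduce.** The 100 subjects come without an effect size, SD, alpha or power. The figure is used below only as an input.

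**Inputs**
- From the protocol: two randomised arms; pre and post scores; 100 subjects.
- Assumed, because the protocol does not say: 1:1 allocation; no dropout; results in SD units; a normal approximation for chance differences.
- Two readings of the 100: all children (n = 50 per arm), or one caregiver counted with each child (50 children, n = 25 per arm).

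**Step 1. Standard error of a difference in mean post scores:** sqrt(2/n) SD.
- n = 50: sqrt(2/50) = 0.200
- n = 25: sqrt(2/25) = 0.283

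**Step 2. Chance of an apparent VR benefit of at least d when there is none:** 1 − Φ(d / SE). At any sample size, VR looks better by some amount half the time. The thresholds of 0.2 and 0.3 SD are illustrative; the protocol sets none.

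| | n = 50 per arm | n = 25 per arm |
|---|---|---|
| d = 0.2 SD | 1 − Φ(1.00) = 15.9% | 1 − Φ(0.71) = 24.0% |
| d = 0.3 SD | 1 − Φ(1.50) = 6.7% | 1 − Φ(1.06) = 14.4% |

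**Step 3. The uncertainty a descriptive comparison leaves unstated:** 95% CI half-width = t(0.975, 2n − 2) × SE.
- n = 50: t on 98 df × 0.200 = 0.397 SD
- n = 25: t on 48 df × 0.283 = 0.569 SD

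A difference of 0.2 or 0.3 SD lies well inside either half-width.

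**Step 4. What the scores already planned could support.** With pre–post correlation r (assumed), variance relative to an unadjusted post score is 1 − r² for analysis of covariance (ANCOVA) and 2(1 − r) for a change score. ANCOVA uses one degree of freedom fewer. Half-widths in SD:

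| r | ANCOVA, n = 50 | Change, n = 50 | ANCOVA, n = 25 | Change, n = 25 |
|---|---|---|---|---|
| 0.3 | 0.379 | 0.470 | 0.543 | 0.673 |
| 0.5 | 0.344 | 0.397 | 0.493 | 0.569 |
| 0.7 | 0.283 | 0.307 | 0.406 | 0.441 |

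At these correlations the baseline-adjusted comparison is more precise than the change score and than the post score (0.397 and 0.569). With the pre score as covariate, modelling the post score or the change gives the same between-arm estimate, so it suits a primary outcome defined before and after the procedure.

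**The case against.** The best defence is that descriptive was loose wording for some statistical comparison. The sentence does speak of comparing effects, and it stands under a heading about measurement. That is possible, but nothing else in the text supports it. The word is attached to the comparison of the interventions, not to baseline characteristics. Even on this reading the sentence needs rewording.

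A reader might infer something stronger: that the trial itself cannot separate a VR effect from chance. The documents do not support that. The arms are randomised and scores are planned before and after the procedure in both, so the data can carry a valid comparison. If the summaries gave n, mean and SD, a reader could work out an unadjusted interval, although the protocol does not promise these and they would not give the baseline-adjusted estimate. The fault lies in the stated analysis and is fully recoverable.

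Two other inferences also go too far. One is that no inferential plan exists: an SAP may exist and is not shown. The other is that the trial has an inflated error rate across its several scales: the protocol plans no tests, so there is no such rate to quote.

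It is also fair to say that ANCOVA is not the only sound choice. A faces scale is ordinal, and the background describes these procedures as causing little pain, so scores may bunch near the floor. This bears on the choice of model, not on the need for an interval and a test.

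**Conclusion.** The point holds as a mismatch between a confirmatory purpose and the only stated method of comparison. That conclusion needs none of the assumed values, because a descriptive difference carries no measure of uncertainty at any sample size.

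The illustration of its size does rest on assumptions: 1:1 allocation, no dropout, SD units and a chosen threshold of 0.2 SD. On those, a spurious VR advantage of that size or more would appear in about 16% of null trials with 50 children per arm and about 24% with 25. The correction should be made, but it is one of wording and analysis: neither the design nor the planned surveys have to change.

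**What to change.** Replace the analysis sentence with text to this effect:

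> Post-procedure child pain will be compared between the arms as randomised, adjusted for the pre-procedure score (for example by ANCOVA), and the difference reported with a 95% CI and p-value. A rank-based or ordinal analysis will serve as a check because the scale is ordinal. Child anxiety (STAIC and Children's Fear Scale, analysed separately) and caregiver STAI will be reported as baseline-adjusted differences with 95% CIs. Descriptive statistics will be used for baseline characteristics.

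Two further edits are needed for the method and purpose to agree:
- State whether child anxiety, which sits under *Primary Outcome*, is primary or supportive.
- Reword the *Purpose* so that it claims to demonstrate an effect only for the outcomes that are formally tested. If the sponsor wants description only, the purpose has to be stated as descriptive or exploratory instead.

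The cost is a few sentences of protocol text, a little more analysis work with a routine model check, and a purpose that may become narrower. No extra patients, visits or surveys are required.

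### Children from age 4 can be randomised to the headset, but the Risks section says the device is not recommended under 13, and the protocol neither links the two nor gives a basis for use below 13.

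*Protocol*

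**What the plan says.** - **Eligibility (Methods, Inclusion Criteria).** The trial takes "Children age 4years old to 17 years old undergoing cast removal, pin removal, or suture removal in clinic". The lower limit is repeated further down the same section: "Minimum Age: 4 years old".
- **Allocation (How do you plan to measure these outcomes?).** The design has two arms, described in this section as follows: "Patients will be randomized to a control group (parental comfort given during the procedure) and the VR group". The procedure is then carried out with whichever of the two was assigned. No age condition is attached to the VR group.
- **Outcome measures (Primary Outcome).** A separate anxiety scale is assigned "For patients less than 7 years old", so young children are expected. Of the pain scale the protocol says: "This scale has been validated to be used in individuals as young as 4 years old to assess their pain".
- **Device (Risks).** The last line of the section reads "The device is not recommended for children under 13". The next heading follows directly, with no comment on the sentence.
- **Size (Methods).** "Number of Subjects to be included in study: 100". Accompanying caregivers are also eligible to take part, and the protocol does not say whether they count towards the 100.

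**The concern.** The eligibility rule and the risk statement address the same children in opposite directions. One admits them to a trial in which they may be assigned the headset; the other says the headset is not recommended for them. A reader who puts the two sections together cannot tell whether use below 13 was a considered decision or an oversight.

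This bears on the safety of the children exposed to the study intervention, and by years of age it concerns most of the eligible range. It is also protocol content: eligibility and device risk are not matters that would be left to a statistical analysis plan.

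**Working it through.** The point is textual, and the plan gives no figure of its own to reproduce. The check has three steps.

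**1. Is there an age limit on the VR arm anywhere?** No. The exclusion criteria contain no age item, and the randomisation text sets no age condition.

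**2. Is a basis for use below 13 given anywhere?** Each candidate was read in turn.

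| Candidate | What it covers | A basis for headset use under 13? |
|---|---|---|
| Validation from age 4 (Primary Outcome) | The pain scale | No; it says nothing about the device |
| Avoiding long use, close observation, five-minute watch, stopping on symptoms (Risks) | Every child in the VR arm, or anyone with symptoms | No; not tied to age and not offered as an answer to the age statement |
| Background and reference list | VR and distraction in general; some titles concern paediatric VR | No; none is cited in support of this device below 13 |
| Exclusion criteria (Methods) | Seizure history, implanted devices and other conditions | No; the age statement is not carried over |

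The last row is informative. Risks discusses seizures, and a history of seizures is an exclusion. Risks warns about implanted devices in conditional terms (consult the doctor or manufacturer first), and implants became an outright exclusion. The age statement carries no condition, yet it led to neither a criterion nor an explanation.

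**3. How much of the trial does it concern?**

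From the protocol, counting whole years of age:
- Eligible ages 4 to 17: 17 − 4 + 1 = 14.
- Under 13, ages 4 to 12: 12 − 4 + 1 = 9, and 9/14 = 64.3%.
- Under 7, ages 4 to 6: 6 − 4 + 1 = 3, and 3/14 = 21.4%.

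These are shares of the age range and need no further assumption. Numbers of children do, because the protocol states neither an age distribution nor an allocation ratio. For illustration, assume 1:1 allocation:

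| Assumed share under 13 | 100 children (50 in VR) | 100 counts caregivers, one per child (25 in VR) |
|---|---|---|
| Even age spread, 9/14 | 50 × 9/14 = 32.1 | 25 × 9/14 = 16.1 |
| 10% | 5 | 2.5 |
| 50% | 25 | 12.5 |
| 80% | 40 | 20 |

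Under the even spread, the children under 7 in the VR arm would number 50 × 3/14 = 10.7, or 25 × 3/14 = 5.4 if caregivers count towards the 100. Counting caregivers halves the head counts only; the percentages do not change.

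**The case against.** The strongest reply is that this is not a strict contradiction. An eligibility rule and a disclosed caution can both be followed: a trial may enrol children outside a device recommendation and say so under Risks. The neighbouring text on implants is worded as advice to a device user, so the age sentence may have been included purely as disclosure. The separate scale for the youngest children suggests that including them was deliberate. The general safeguards do reduce exposure and help to detect harm in younger children too. The protocol carries an ethics approval date, and a rationale may exist in the ethics application or the consent pages, neither of which can be seen here. Finally, the protocol names no harm specific to children under 13; the nearest statement is that light-triggered seizures are commoner in the young.

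Much of this stands as qualification. The sentence is a caution, no ban is breached, and no claim can be made about what families or the ethics board were told. The head counts are illustrative. But none of it reconciles the two sections. Approval of a version that contains both statements does not put a reason into the text, and safeguards that apply to every child do not explain why the device is used in those for whom it is not recommended. Even if inclusion was deliberate, the protocol does not say so or say why.

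**Conclusion.** The concern holds and must be fixed. Children aged 4 to 12, who make up 9 of the 14 eligible years of age (64%), may be assigned a headset that the protocol's own Risks section does not recommend for them, and no part of the protocol connects the two statements or gives a basis.

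That conclusion rests on the text alone. Only the head counts depend on assumptions: about 32 of 50 VR children with an even age spread, 25 to 40 at assumed shares of 50% to 80%, and 5 at an assumed 10%; about half of each if the 100 includes caregivers. The conflict would remain at any share above zero.

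**What to change.** Reconcile the age criterion and minimum age in Methods with the device statement in Risks, and state in the protocol the basis for whatever is decided. Check that the consent and assent wording agrees; those pages were not available for this review. No age rule is proposed here: that decision belongs to the investigator and the ethics board.

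The cost is one protocol amendment touching two sections, plus the consent check. If an adequate basis already exists, writing it down needs no new data, visits or procedures; the protocol does not show whether it does. If the reconciliation changed the age range, the recruitment pool would change with it.
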